Pectoral nerve blocks or PECS block is an emerging regional technique that has proven to be effective in comparison to paravertebral blocks in patients undergoing breast surgery and mastectomy with reduced perioperative opioid consumption and improved pain scores.

The lateral pectoral nerve, medial pectoral nerve, intercostal nerves and long thoracic nerve are all targets for the PECS block. It can be safely performed under ultrasound guidance.

 Mount Sinai	Protocol Name:	COMPARISON BETWEEN PECS BLOCK AND LOCAL SURGICAL INFILTRATION IN ROBOTIC VIDEO ASSISTED THORACOSCOPIC SURGERY- A RANDOMISED CONTROLLED TRIAL
	Principal Investigator:	[name] [name].
	Primary Contact Name/Contact Info:	[name]. [REDACTED]
	Date Revised:	07/08/2017
	Study Number:	IF2058656/HSM# 17-00611/GCO#17-1294

The purpose of our study is to evaluate the difference in quality of analgesia between efficacy of PECS block and local surgical infiltration by surgeon as measured by patient opioid consumption and pain scores.

1)Objectives

Research Question: Does PECS block provide superior analgesia in comparison with surgeon injected local infiltration into the wound in a robotic assisted VATS?

Primary outcome: The amount of opioid consumption (in mg IV morphine equivalents) postoperatively up to 24 hours after the end of procedure. The degree of postoperative pain in terms of VAS at rest and on cough on arrival to PACU, 2 hours later, discharge from PACU, 6 hours, 12 hours, 18 hours and 24 hours after surgery.

Secondary outcome:

Time to first dose of narcotic administration, PACU or ICU length of stay, and patient satisfaction.

2)Background

See above. There have been several studies regarding efficacy of local infiltration of wound in thoracic surgery for pain control. PECS block is a novel technique used in pain control in patients undergoing mastectomy. But there have been no study to date comparing the use of local infiltration and PECS block in thoracic surgery.

3)Setting of the Human Research

Prospective triple blinded randomized control trial undergoing robotic assisted VATS. The research study will take place at Mount Sinai West hospital. The site PI is [name], MPH.

 Mount Sinai	Protocol Name:	COMPARISON BETWEEN PECS BLOCK AND LOCAL SURGICAL INFILTRATION IN ROBOTIC VIDEO ASSISTED THORACOSCOPIC SURGERY- A RANDOMISED CONTROLLED TRIAL
	Principal Investigator:	[name] [name].
	Primary Contact Name/Contact Info:	[name]. [REDACTED]
	Date Revised:	07/08/2017
	Study Number:	IF2058656/HSM# 17-00611/GCO#17-1294

4)Resources Available to Conduct the Human Research

For n=100, the feasibility of recruitment is manageable. With the HIPAA waiver requested, the surgeon will provide investigators (both of whom are physicians within the department of Anesthesiology) with information of eligible patients. The surgeon will also provide study information (protocol, consent, general information) to patients in the surgeon’s office. After the operating room schedule has been reviewed for potential participants in the study the contact information will be obtained through the surgeon’s office. Subjects will be called by the department of Anesthesiology when their surgery is scheduled. A member of the research team will contact the patient to explain the study, confirm participation, and answer any questions. On the day of the surgery, the subject will meet the research team in the holding area. The team will finalize participation and ask the subject to sign study consent forms. The staff members on this protocol are all employees of Mount Sinai and will either be a resident or attending physicians that are included on the IRB protocol. There are two primary members of the research personnel:

a)[name], MPH – Roles for [name] in this study include serving as primary investigator responsible for study design and planning, data collection, subject recruitment, manuscript writing and preparation, data analysis, safety monitoring, and responding to adverse events and/or complications. He is certified in PPHS/IRB protocols, all Citi/IRB required training in human subject protection, and has prior clinical research experience. He is also a board certified anesthesiologist and assistant professor of anesthesiology with the Icahn School of Medicine and the Mount Sinai Health System.

b)[name] – Roles for [name] include serving as primary research coordinator involved in data collection, subject recruitment, manuscript writing and preparation, data analysis, safety monitoring, and responding to adverse events and/or complications. She has completed all of her required CITI training to be IRB certified and has experience in clinical research. In addition she has been a resident physician in anesthesiology with the Icahn School of Medicine in good standing for the previous two years going on her third.

 Mount Sinai	Protocol Name:	COMPARISON BETWEEN PECS BLOCK AND LOCAL SURGICAL INFILTRATION IN ROBOTIC VIDEO ASSISTED THORACOSCOPIC SURGERY- A RANDOMISED CONTROLLED TRIAL
	Principal Investigator:	[name] [name].
	Primary Contact Name/Contact Info:	[name]. [REDACTED]
	Date Revised:	07/08/2017
	Study Number:	IF2058656/HSM# 17-00611/GCO#17-1294

There are institutional processes to ensure that all persons assisting with the protocol will be well informed. The research personnel will conduct regular meetings and department email updates to review the results and safety data of the study. The research personnel will initiate the formation of a safety monitoring board for adverse effects, complications, or complaints from patient subjects.

5) Study Design

Prospective triple blinded randomized control trial. With the HIPAA waiver requested, the surgeon will provide the investigators (both of them are physicians within the Department of Anesthesiology) with information of eligible patients. The surgeon will also provide study information (protocol, consent, general information) to patients in the surgeon's office. After the operating room schedule has been reviewed for potential participants in the study the contact information will be obtained through the surgeon's office. Subjects will be called by the department of Anesthesiology when their surgery is scheduled. A member of the research team will contact the patient to explain the study, confirm participation, and answer any questions. On the day of the surgery, the subject will meet the research team in the holding area. The team will finalize participation and ask the subject to sign study consent forms. All patients will be provided with copies of the IRB protocol and consent if they wish to have it. Copy of the consent form will be sent in a secured email to the potential subject. The email will be secured by entering in [SECURE] in the e-mail subject line. Once recruited blinding assessments will be done by the study team.

Patients will be assigned randomly using a computer-generated table of numbers to either PECS (Pecs group) or placebo (placebo group). Block team will perform all blocks. Resident anesthesiologist will know the group allocation but will not be involved in the study and prepare the placebo and anesthetic solutions. Patients assigned to PECS block group will receive 30ml 0.25% bupivacaine under ultrasound guidance on the side of surgery. Otherwise, the patient, surgeon, and anesthesiologist in the case will be blinded. At the conclusion of the surgery prior to skin closure, all the patients will receive 20ml of local anesthetic infiltration as per surgeon's current practice.

a) Recruitment methods: See above.

 Mount Sinai	Protocol Name:	COMPARISON BETWEEN PECS BLOCK AND LOCAL SURGICAL INFILTRATION IN ROBOTIC VIDEO ASSISTED THORACOSCOPIC SURGERY- A RANDOMISED CONTROLLED TRIAL
	Principal Investigator:	[name] [name].
	Primary Contact Name/Contact Info:	[name]. [REDACTED]
	Date Revised:	07/08/2017
	Study Number:	IF2058656/HSM# 17-00611/GCO#17-1294

b)Inclusion and Exclusion Criteria

Inclusion criteria: ASA (American Society of Anesthesiology) class I-IV, age 18-75.

Exclusion criteria: ASA class V, morbid obesity, patient refusal, patients with chronic pain or on pain medications, allergy to LA, patients receiving any additional regional techniques, coagulopathy, patients receiving systemic anticoagulation, local infection, and procedures anticipated to last more than 5 hours.

c)Number of Subjects

We intend to have an n=100. Based on a confidence level of 95% with a Z score of 1.96, standard deviation of .5 and a confidence interval of 10% our sample size should be 96. For ease of statistical calculations we rounded up to 100 patients. Based on previous literature pertaining to local infiltration in thoracic surgery and postoperative analgesia using PECS block in breast surgery, we found studies included anywhere from 85 to 113 patients which is consistent with our calculations.

$$Z^2 * (p) * (1-p)$$

ss =

$$c^2$$

Where:

Z = Z value (1.96 for 95% confidence level)
 p = percentage picking a choice, expressed as decimal (.5 used for sample size needed)
 c = confidence interval, expressed as decimal (e.g., .01= ±1)

Sample size= [(1.96^2)(.5)(.5)]/(.1^2)=96 subjects

For effect size, we expect a Cos d medium effect of 0.5. The estimate for sample sizes was obtained by using the first set of pain scores obtained in the PACU.

 Mount Sinai	Protocol Name:	COMPARISON BETWEEN PECS BLOCK AND LOCAL SURGICAL INFILTRATION IN ROBOTIC VIDEO ASSISTED THORACOSCOPIC SURGERY- A RANDOMISED CONTROLLED TRIAL
	Principal Investigator:	[name] [name].
	Primary Contact Name/Contact Info:	[name]. [REDACTED]
	Date Revised:	07/08/2017
	Study Number:	IF2058656/HSM# 17-00611/GCO#17-1294

d)Study Timelines

2017-2018 and subsequent data analysis. The subject’s participation will be from time of enrollment in the pre-operative period until first postoperative day. Estimated date of enrollment completion will be when 100 eligible subjects are enrolled in final data analysis. Estimate date for study completion will be June 2018.

e)Endpoints

The primary endpoints will be the amount of opioid consumption (in mg IV morphine equivalents) postoperatively up to 24 hours after the end of procedure and the degree of postoperative pain in terms of VAS at rest and on cough on arrival to PACU, 2 hours later, discharge from PACU, 6 hours, 12 hours, 18 hours and 24 hours after surgery.

Secondary end points – Time to first dose of narcotic administration, PACU or ICU length of stay, and patient satisfaction.

Conclusion of data analysis and evaluation of significance of findings will follow completion of data collection on primary and secondary outcomes.

f)Procedures Involved in the Human Research

Prospective randomized controlled trial and data analysis only. PECS block and local wound infiltration. Intraoperative care of the patient will be provided by an anesthesia team member who is a part of the Mount Sinai System. The anesthesia provider will not be aware of the randomization of the patient. Standard post-operative orders will be written for patients during their time in the PACU. Orders include oxycodone, fentanyl and hydromorphone.

g)Specimen Banking

N/A

 Mount Sinai	Protocol Name:	COMPARISON BETWEEN PECS BLOCK AND LOCAL SURGICAL INFILTRATION IN ROBOTIC VIDEO ASSISTED THORACOSCOPIC SURGERY- A RANDOMISED CONTROLLED TRIAL
	Principal Investigator:	[name] [name].
	Primary Contact Name/Contact Info:	[name]. [REDACTED]
	Date Revised:	07/08/2017
	Study Number:	IF2058656/HSM# 17-00611/GCO#17-1294

h)Data Management and Confidentiality

Data collected in excel file to be de-identified after initial collection. Excel file be subsequently encrypted and shared only between the two above listed investigators via secure Mount Sinai electronic mail.

The information included in the data will be medical record number, age, gender, ASA class, type of surgery, pain score assessments; time to first narcotic, total narcotic use and pain scores up to 24 hours after surgery. Only the research personnel will have access to the data. The data will be stored as a hard copy files and on a secure spreadsheet. The research personnel is responsible for the receipt of the data. The PI will keep the hard copies secure and any electronic data will be encrypted. No personal identifiers will be used. The data will undergo statistical analysis.

i)Provisions to Monitor the Data to Ensure the Safety of Subjects

Part I: Elements of Data and Safety Monitoring Plan

MSSM Principal Monitor:

Last Name: [name]

First Name: [name]

Academic Title: Attending Physician, Assistant Professor

Department: Anesthesiology

Mailing Address: Mount Sinai West [name]

[contact]

Fax:

E-mail: [contact]

MSSM Additional Monitor:

Last Name: [name]

First Name: [name]

Academic Title: Research Personnel, Physician

Department: Anesthesiology

Mailing Address: Mount Sinai West [name]

[contact]

Fax:

 Mount Sinai	Protocol Name:	COMPARISON BETWEEN PECS BLOCK AND LOCAL SURGICAL INFILTRATION IN ROBOTIC VIDEO ASSISTED THORACOSCOPIC SURGERY- A RANDOMISED CONTROLLED TRIAL
	Principal Investigator:	[name] [name].
	Primary Contact Name/Contact Info:	[name]. [REDACTED]
	Date Revised:	07/08/2017
	Study Number:	IF2058656/HSM# 17-00611/GCO#17-1294

E-mail: [contact]

The principal monitor is a board certified anesthesiologist thus minimizing the risk to the subjects and further optimizing their health and wellbeing. Adverse events will be monitored as a standard of care everyone receives regardless of participation in the study. The safety and data information will be reviewed on a daily basis until the desired sample size is achieved. All temporary and/or permanent suspensions will be reported.

j)Withdrawal of Subjects

Patients may withdraw from the study at any given time by contacting any member of the research study group. Data will not be collected on patients who wish to withdraw. Patient do not need to withdraw consent in writing.

6)Risks to Subjects

If patients are injured or made sick from taking part in this research study, medical care will be provided. Generally, this care will be billed to the patient or their insurance in the ordinary manner and the patient will be responsible for all treatment costs not covered insurance, including deductibles, co-payments and coinsurance. This does not prevent the patient from seeking payment for injury related to malpractice or negligence. Contact the investigator for more information.

As with any medication, there is a possibility of an allergic reaction. Although rare, possible complications include LA toxicity, hypersensitivity reaction, bleeding or local site infection, chance of pneumothorax. All anesthesiologists involved in patient care will be prepared for the prevention and rescue for any complications involving local anesthetic injections.

7)Provisions for Research Related Harm/Injury

If patients are injured or made sick from taking part in this research study, medical care will be provided. Generally, this care will be billed to the patient or their insurance in the ordinary manner and the patient will be responsible for all treatment costs not covered insurance, including deductibles, co-payments and coinsurance. This does not prevent the

 Mount Sinai	Protocol Name:	COMPARISON BETWEEN PECS BLOCK AND LOCAL SURGICAL INFILTRATION IN ROBOTIC VIDEO ASSISTED THORACOSCOPIC SURGERY- A RANDOMISED CONTROLLED TRIAL
	Principal Investigator:	[name] [name].
	Primary Contact Name/Contact Info:	[name]. [REDACTED]
	Date Revised:	07/08/2017
	Study Number:	IF2058656/HSM# 17-00611/GCO#17-1294

patient from seeking payment for injury related to malpractice or negligence. Contact the investigator for more information.

8)Potential Benefits to Subjects

It is important to know that patients may not get any benefit from taking part in this research. However, possible benefits may be improved knowledge about how the different forms of analgesia affect pain control in thoracic surgery. There is potential for better pain control for the surgery.

9)Provisions to Protect the Privacy Interests of Subjects

Patients will be appropriately educated about the research study. Any questions or concerns they have will be adequately addressed and patients will have the option to decline participation. Patients will be given as much time as they need to review the consent form. The study personnel will be approaching the subjects. Privacy will be maintained by not including any identifiers such as names or addresses in the data collected.

The identities of human subjects whose data is being studied will be de-identified as per HIPAA Privacy Rule.

10)Economic Impact on Subjects

Patients will not incur any additional cost for participating in the study. The medications used are part of a standard anesthetic regimen that will be billed to subject's insurance as bundled standard of anesthesia care. The cost of the procedure is overall unaffected.

11)Payments to Subjects

Patients will not be reimbursed for their participation.

12)Consent Process

 Mount Sinai	Protocol Name:	COMPARISON BETWEEN PECS BLOCK AND LOCAL SURGICAL INFILTRATION IN ROBOTIC VIDEO ASSISTED THORACOSCOPIC SURGERY- A RANDOMISED CONTROLLED TRIAL
	Principal Investigator:	[name] [name].
	Primary Contact Name/Contact Info:	[name] [REDACTED]
	Date Revised:	07/08/2017
	Study Number:	IF2058656/HSM# 17-00611/GCO#17-1294

Informed consent will be obtained prior to the procedure. Both the HRP-090 (SOP) Informed Consent Process for Research and the HRP-091 (SOP) Written Documentation of Consent will be followed by the study team. These documents are both available at <http://icahn.mssm.edu/research/resources/program-for-the-protection-of-human-subjects/irb-members-palette>.

13) Process to Document Consent in Writing

The patients will receive a paper copy of the IRB approved consent packet and will sign in the designated areas to confirm consent of participation. They will have the option of have a copy of the consent and may ask for a personal copy of the consent.

14) Vulnerable Populations

Indicate specifically whether you will include (target) or exclude each of the following populations:

Include	Exclude	Vulnerable Population Type
	X	Adults unable to consent
	X	Individuals who are not yet adults (e.g. infants, children, teenagers)
	X	Wards of the State (e.g. foster children)
	X	Pregnant women
	X	Prisoners

15) Multi-Site Human Research (Coordinating Center)

This study will be performed within the Mount Sinai West Hospitals. No additional centers will be involved.

16) Community-Based Participatory Research

 Mount Sinai	Protocol Name:	COMPARISON BETWEEN PECS BLOCK AND LOCAL SURGICAL INFILTRATION IN ROBOTIC VIDEO ASSISTED THORACOSCOPIC SURGERY- A RANDOMISED CONTROLLED TRIAL
	Principal Investigator:	[name] [name].
	Primary Contact Name/Contact Info:	[name]. [REDACTED]
	Date Revised:	07/08/2017
	Study Number:	IF2058656/HSM# 17-00611/GCO#17-1294

This does not apply to our study.

17)Sharing of Results with Subjects

Results will not be shared with the patients since the study will take time to complete. Patients can request results if they contact the PI by writing.

18)External IRB Review History

This does not apply to our study.

19)Control of Drugs, Biologics, or Devices

Not applicable. Local anesthetic are routinely used in this setting.

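### The stated question sets PECS block against surgeon infiltration, but every patient receives infiltration, so only the effect of adding PECS can be estimated

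*Combined protocol and SAP*

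**What the plan says.** The front part of the protocol describes a head-to-head trial.

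- The title announces a comparison between PECS block and local surgical infiltration.
- The purpose statement before section 1 is to "evaluate the difference in quality of analgesia between efficacy of PECS block and local surgical infiltration by surgeon".
- The research question in section 1 (Objectives) is "Does PECS block provide superior analgesia in comparison with surgeon injected local infiltration into the wound in a robotic assisted VATS".
- Section 2 (Background) gives the evidence gap: "But there have been no study to date comparing the use of local infiltration and PECS block in thoracic surgery".

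Section 5 (Study Design) describes different arms.

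- Patients are randomised "to either PECS (Pecs group) or placebo (placebo group").
- A resident who is otherwise outside the study is to "prepare the placebo and anesthetic solutions".
- For the active arm: "Patients assigned to PECS block group will receive 30ml 0.25% bupivacaine under ultrasound guidance on the side of surgery".
- Before skin closure, "all the patients will receive 20ml of local anesthetic infiltration", following the surgeon's usual routine.

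Section 5 f) (Procedures) lists the block and the infiltration together without saying who receives which.

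**The concern.** The purpose and the research question oppose two treatments. In the arms as written, one of those treatments is given to everybody. The placebo arm does receive the comparator named in the question, but so does the PECS arm. A difference between arms can then be credited to PECS on top of infiltration, not to PECS in place of it.

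The risk lies in the conclusion. No section states an estimand, a statistical hypothesis or a limit on what may be concluded. A favourable result, read against the research question, would be reported as PECS being superior to infiltration. A reader could take that as grounds for using one instead of the other, which the trial does not test.

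**Working it through.** **Step 1: what each arm receives (section 5, Study Design).**

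| Arm | Randomised injection | Infiltration before closure |
|---|---|---|
| PECS | 30 ml 0.25% bupivacaine | 20 ml local anesthetic |
| Placebo | placebo | 20 ml local anesthetic |

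The infiltration column is the same in both rows. The only randomised difference is the PECS injection versus placebo. No section describes PECS without infiltration, or restricts infiltration to one arm. The mention of placebo solutions does not change this, because the infiltrate is stated to be local anesthetic for all patients.

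**Step 2: counts.** Planned n = 100 (section 5 c). Patients to be infiltrated: 100. Patients assigned PECS without infiltration: 0. The allocation ratio is not stated; if it is 1:1 (assumption), each arm has 100 / 2 = 50.

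**Step 3: the plan's own figure.** Section 5 c) computes 1.96² × 0.5 × 0.5 / 0.1² = 96.04, that is 96, rounded up to 100. This reproduces. It is a precision formula for a single proportion and contains no between-arm contrast, so it does not show which comparison was meant. The standardised effect of 0.5 quoted after it is not tied to a contrast either.

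**Step 4: the two effects.** Let B(·) be the benefit of a regimen.

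- Add-on effect, which the arms estimate: B(PECS + infiltration) - B(infiltration)
- Head-to-head effect, which the question asks for: B(PECS) - B(infiltration)
- Subtracting: head-to-head = add-on - x, where x = B(PECS + infiltration) - B(PECS)

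Here x is the benefit of infiltration in patients who already have PECS. Estimating it needs patients with PECS alone, and there are none. A larger sample would not help, because the missing quantity is an arm and not precision.

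**Step 5: illustration.** Take the protocol's 0.5 SD as the add-on effect (assumption) and let x vary over assumed values:

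| x (SD, assumed) | Head-to-head = 0.5 - x (SD) |
|---|---|
| 0 | 0.5 |
| 0.25 | 0.25 |
| 0.5 | 0 |
| 0.75 | -0.25 |

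The same trial result fits PECS being better than, equal to, or worse than infiltration.

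**The case against.** The strongest reply is that the head-to-head wording is shorthand. Infiltration is described as the surgeon's usual routine, so it can be read as background care kept for everyone, with PECS or placebo added. On that reading the placebo arm is the usual-care comparator, the design is sound and only the wording is loose. The protocol never speaks of omitting infiltration, and the patient benefit it suggests in section 8, possibly better pain control, fits an add-on. Since the repair may be wording alone, a lower severity could be argued.

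Much of this is right. The usual-care phrase supports the add-on reading of the arms, and the add-on contrast is valid and useful. But nothing in the title, purpose or question says that PECS is added to infiltration. If shorthand was meant, the wording correction is exactly what is needed. Severity stays high because the mismatch sits in the primary question and governs what the trial may claim.

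Two smaller objections also have force. The SD values rest on a freely chosen x, and the 0.5 is not stated to be an add-on effect, so the second table shows what is possible and does not measure the size of the problem. The Background sentence describes earlier literature, not this trial's arms, so it is not itself an error.

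**Conclusion.** The concern holds. As written, the trial estimates the effect of adding PECS to infiltration and cannot answer whether PECS is superior to infiltration. The mismatch affects the whole trial: 100 of 100 planned patients are to be infiltrated and 0 are assigned PECS alone. This follows from the text of section 5 and needs no numerical assumption. The 50 per arm rests on assumed 1:1 allocation. The head-to-head range of +0.5 to -0.25 SD rests on an assumed add-on effect of 0.5 SD and assumed x of 0 to 0.75 SD. The conclusion depends on none of these.

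**What to change.** Reconcile the title, purpose statement and section 1 with the arms in section 5.

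**If the section 5 arms stand:**

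- Reword the title and purpose to describe PECS added to surgeon infiltration.
- Restate the research question along these lines: *Does adding a PECS block to surgeon infiltration improve analgesia (24-hour opioid consumption and VAS pain at rest and on cough) compared with placebo plus surgeon infiltration?* This keeps both primary outcomes in section 5 e), including "the degree of postoperative pain in terms of VAS at rest and on cough on arrival to PACU" and the later time points.
- Add a sentence that conclusions are limited to the add-on effect, and that PECS as a replacement for infiltration is not tested.
- The Background sentence may stay as a description of the literature, but the trial should not be presented as filling that gap.

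The cost is wording only. Procedures, arms and data collection do not change; the headline claim becomes narrower.

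**If a head-to-head comparison was intended:** the section 5 arms do not deliver it, and the investigators must resolve the conflict before keeping the question. That is a design change. The arms, and with them the blinding and sample size, would have to be revisited. The sample-size formula contains no between-arm contrast and needs attention in either case; that is a separate point. Which regimen patients should receive is for the investigators to decide, not this review.

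### Do the planned meetings, department emails and daily data review endanger the blind?

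*Combined protocol and SAP*

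**What the plan says.** Section 4 (Resources), in a paragraph about keeping those who assist with the protocol informed, has the research personnel hold "regular meetings and department email updates to review the results and safety data of the study". It gives no recipients, dates or format. The same paragraph plans a safety monitoring board for adverse effects, complications and complaints.

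Section 5(i) (safety monitoring) says: "The safety and data information will be reviewed on a daily basis until the desired sample size is achieved".

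Other sections bear on who sees what, and when:

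- Section 5(h): the encrypted Excel file is "shared only between the two above listed investigators via secure Mount Sinai electronic mail", and "Only the research personnel will have access to the data".
- Section 5(e): "evaluation of significance of findings will follow completion of data collection on primary and secondary outcomes".
- Section 5 (Study Design): "Resident anesthesiologist will know the group allocation but will not be involved in the study". The patient, the surgeon and the anesthesiologist in the case are blinded.
- Section 4: the duties of each of the two primary research personnel include "data collection, subject recruitment, manuscript writing and preparation, data analysis, safety monitoring". On recruitment it says: "Subjects will be called by the department of Anesthesiology when their surgery is scheduled".

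**The concern.** Section 4 names results separately from safety data, so the word seems to mean more than adverse events. The daily review runs during accrual. Nothing states that either activity is confined to data pooled over arms. An email to a department also seems to reach more people than the access limits in Section 5(h) allow.

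The endpoints make this worth asking. VAS scores are patient-reported, and opioid use depends partly on staff dosing decisions. The people who review the data also recruit, collect data and analyse, and they belong to the department that provides anesthesia. If outcome trends by arm reached staff who treat or assess patients, and those staff then guessed a patient's group, both primary endpoints could be coloured by expectation. Repeated looks at results also raise the question of type I error.

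**Working it through.** The question is mainly one of reading sections together, with two small pieces of arithmetic.

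**1. Do the sections conflict on access?**

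- *Daily review, Section 5(i), against Section 5(h).* The two monitors appear, from the titles and department given, to be the two research personnel. Section 5(h) allows them the data, and as data collectors they see it anyway. There is no conflict over who sees it.
- *Department emails, Section 4, against Section 5(h).* The limits in 5(h) concern the Excel file and access to the data. A short summary can be emailed without sending that file. Recipients are not named, and the email could be among research personnel only. The introductory sentence of that paragraph points to a wider audience. This is an ambiguity and not a clear contradiction.

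**2. Would the reviewed material carry arm labels?**

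Three statements suggest not:

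- The resident who prepares the solutions and knows the allocation is outside the study (Section 5).
- The fields listed in Section 5(h) are record number, age, gender, ASA class, type of surgery, pain scores, time to first narcotic and total narcotic use. Treatment group is not among them. The list also omits length of stay and satisfaction, so it is evidence and not an explicit restriction.
- Significance is evaluated after collection of the primary and secondary outcomes (Section 5(e)).

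**3. What could a pooled summary reveal?**

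Inputs: standardised effect 0.5 (Section 5(c)) and N = 100 (Section 5(c)). Equal arms are assumed, because no allocation ratio is stated.

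- The pooled mean is (mean A + mean B)/2. Any difference between arms is compatible with the same pooled mean.
- The pooled variance is σ² + (δ/2)². With δ = 0.5σ this is σ²(1 + 0.25²) = 1.0625σ². The pooled SD is √1.0625 = 1.031 times the within-arm SD, about 3% larger.
- For roughly normal data, the relative standard error of an SD from 100 patients is about 1/√(2 × 99) = 0.071, or 7%.

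The trace of a treatment effect in pooled data is less than half of its own sampling error, even at full enrolment. It also says nothing about which group a given patient is in.

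**4. Do the looks affect type I error?**

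The size is fixed at 100, no stopping rule is attached to any review, and there is one evaluation at the end. A look that triggers no decision cannot change the probability of rejection, so for a single endpoint it stays at α. The protocol states a 95% confidence level but no test level, so α = 5% is assumed. A simulation of 100,000 null trials with 50 per arm and one final t-test gave 4.9%. Inflation would require arms to be compared at each look and the result acted on, which no section describes.

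**5. Does the recruitment route add a risk?**

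A patient being called about participation has no group yet, and nothing suggests that upcoming assignments are known. The sentence after the one on departmental calls gives the contact to a member of the research team. Guessed allocation cannot steer who is approached.

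**The case for a change.** The strongest reply is that the plan never says outright that by-arm summaries wait until the end. Analysis needs the allocation, and no section says when it is joined to the outcome data. The people named as blinded are the patient, the surgeon and the anesthesia provider. Data collectors and analysts are not named, although the trial is called triple blinded, and the safety board has no stated membership or independence. A plan for circulating results to a department, with subjective endpoints, should arguably not leave this to inference.

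That stands as a description of what is unstated. It does not show that the plan, followed as written, would go wrong. Each step of the harm has to be supplied from outside the text: that allocation is joined early, that results are split by arm, that these reach staff who treat or assess, and that those staff guess groups. A rule against circulating any outcome summary, pooled ones included, would go further than the concern supports, since pooled figures do not unblind.

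**Conclusion.** No change to the plan is needed. Section 4 leaves the content, recipients and timing of the updates undefined and is loosely aligned with Section 5(h). This is missing detail, and a team running a blinded trial would fill it in the ordinary way: updates on accrual, completeness and safety, with outcomes not split by arm until collection is complete. The daily review already fits the access limits.

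No bias is demonstrated, and none can be quantified from the documents. The effect on type I error is nil as the plan is written. The conclusion rests on three assumptions: allocation stays with the person outside the study until data collection is complete, as Sections 5 and 5(e) imply; no review triggers a stopping decision based on outcomes; and the test level is 5%. If results were in fact produced by arm during accrual, the point would have to be reopened.
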